### 11.6 Trial Design

This is an open-label, parallel design study of 12 and 24 weeks of sofosbuvir/velpatasvir. Subjects are initially started on NHS standard of care treatment, and are consented to participate between treatment week 8-12 (of the standard 12 week course). This design is chosen for several reasons:

- To maximise the time between fulfilling entry criteria (i.e. week 2 ≥ 30iu/mL) and consent, to allow subjects time to consider participation
- Given sofosbuvir/velpatasvir is generally well tolerated, early discontinuation is usually due to non-adherence. By recruiting patients after at least 8 weeks, the study is more likely to recruit subjects willing to adhere to extended treatment. The study specifies that subjects have taken at least 90% of prescribed drugs by screening
- Sofosbuvir/velpatasvir is an expensive treatment and in order to prevent wastage of prescribed NHS treatment when subjects commence on the trial, they are recruited only after the final prescription (each prescription is for one bottle of sofosbuvir/velpatasvir which contains 4 weeks of drug) has been dispensed at treatment week 8. Therefore, only subjects randomised to extended treatment will be dispensed with study drugs.

Maximum duration of participation is 16 weeks for Arm A (12 weeks treatment) - 4 weeks of observation during standard of care treatment, 12 weeks of follow-up, and 28 weeks for Arm B (24 week treatment arm) – 16 weeks of study treatment (4 weeks of standard of care treatment plus 12 weeks of additional IMP treatment), 12 weeks of follow-up.

Treatment week 0 is defined as commencement of sofosbuvir/velpatasvir on NHS treatment programme, before enrolment into the study. Subjects can be pre-screened for study eligibility once week 2 virological response becomes available. Patient information sheet can be provided to interested subjects, but they cannot be consented to participate until week 8 of treatment. Screening and randomisation can take place until the end of standard treatment at week 12.

Upon enrolment into the study until treatment week 12, subjects will proceed according to protocol but they will complete drugs prescribed as part of NHS treatment prior to enrolment. This is in order to reduce wastage of high cost drugs. Sites must ensure sufficient time between enrolment and end of 12 weeks treatment, to dispense additional IMP for participants randomised to arm B (24 weeks).

Study visits are as follows:

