#### 13.5 Patient Allocation

#### 13.5.1 Randomisation Method

Participants who fulfill inclusion/ exclusion criteria will be randomised. This takes place anytime after enrolment between treatment week 8 to 12. Sites must ensure sufficient time to randomise participants and dispense additional IMP for those in the arm B (24 weeks) such that there will not be more than 24 hours before commencing week 13 treatment.

Participants will be allocated into treatment arms A and B in a 1:1 ratio, by block randomisation, and stratified by whether they have compensated cirrhosis or decompensated cirrhosis at baseline. Participants with previous history of decompensation will be considered as having decompensated cirrhosis for the purpose of stratification. This is in order to generate equal numbers within each arm, with balanced severity of liver disease distributed. Clinical trial data suggests that severity of liver disease and presence of decompensated cirrhosis are one of the most important factors determining treatment outcome [8].

There may be other patient factors which influence treatment success, but further stratification for a study of 60 participants would not be appropriate. Block randomisation will enable interim analysis to be performed with balanced groups.

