#### 13.9 Withdrawal criteria

Participants have the right to withdraw consent for study participation at any time. Participants will be informed before enrolment that if they wish to withdraw from the study, or if they are withdrawn for any reasons (such as those listed below), study treatments will be discontinued and no further study procedures or visits will be performed. However, participants will be asked at enrolment to consent to having their treatment virological outcome (SVR at 12 weeks after treatment discontinuation) collected, if available. Participants can opt to withdraw this consent, and withdraw

completely from the study; at this point no further data will be collected. Data obtained up to the point of withdrawal will be kept.

When a participant is withdrawn from the study, this is recorded in the medical notes, along with his or her consent (or withdrawal of consent) for collection of treatment virological outcome data.

Participants who withdraw from the study will be notified that they will discontinue treatment with study drugs, and unused study drugs must be returned. They have the option to continue treatment with sofosbuvir/velpatasvir (or other HCV treatment regimes) as routine NHS standard of care at the discretion of their usual clinician. If a participant withdraws during treatment week 8-12, while taking the NHS-supplied sofosbuvir/velpatasvir, the drugs should be returned according to the local NHS pharmacy policy and they may continue to use the drugs on the advice of their usual clinician.

Participants who experience intolerable toxicity or for other clinical reasons according to the investigator can discontinue the study drugs. Dose reduction of sofosbuvir/velpatasvir is not permitted. Participants who discontinue treatment can remain on the study (for follow up) provided they do not withdraw consent.

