#### 15.0 Trial Medication

# 15.1 Name and description of investigational medicinal product(s)

This study involves the use of two medications in a fixed dose combination – Epclusa 400mg/100mg film-coated tablet, which contains 400mg sofosbuvir and 100mg velpatasvir.

Dose reduction is not permitted but discontinuation, at the discretion of the participant or investigator, is permitted. This must be documented in the participant medical notes and reported on CRF.

All subjects will initially start treatment with sofosbuvir/velpatasvir outside of the study, on the NHS treatment programme. Subjects must not have taken ribavirin along with sofosbuvir/velpatasvir. Subjects are recruited during NHS treatment period, between treatment weeks 8-12. Therefore, subjects have been dispensed with their 3rd prescription of sofosbuvir/velpatasvir (supplied as 28 tablets per bottle – i.e. one bottle every 4 weeks) by the time of study enrolment. In order to avoid wastage of high cost drugs when patients enter this study, they will continue to take the dispensed supply between weeks 8 to 12. Subjects randomised to the 12 week arm (Arm A) will receive no further drug supply. Subjects randomised to the extended treatment will receive additional study drug for weeks 13-24. (Arm B)

Study drugs (only required for weeks 13-24) will be supplied in their original manufacturer's packaging, which ensures the integrity of the product during transport and storage. Study drugs will be labelled at the site trial pharmacy (or delegate) with approved clinical trial labels in accordance with Annex 13. It should contain:

- participant's study details
- dosing instructions
- contact details for study investigator
- the phrase 'keep out of reach of children'
- the phrase 'for clinical trial use only'
- trial reference code (EudraCT number)

The original manufacturer's Patient Information Leaflet will be provided.

Each dispensing episode will be for a 4 week supply. Patients are to return the IMP container before the next 4 weeks is dispensed.

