# 19.0 Statistical and Data Analysis

#### 19.1 Sample size calculation

The planned sample size is 60 participants - with 30 participants in each of two treatment arms. This is based on the assumption of a 30% difference in the primary outcome measure (proportion of patients who achieve SVR12) between the two treatment arms, where SVR in the 12 week treatment arm is 65%, and 95% in the 24 week treatment arm. All outcomes are measured on an intention to treat basis.

Estimates of SVR rates for patients with slow treatment response (week 2 HCV detectable) is derived from post-hoc analyses of cohort studies or clinical trials. For genotype 3 patients with decompensated cirrhosis treated with sofosbuvir and NS5A inhibitor (daclatasvir or ledipasvir) with or without ribavirin, SVR was 65% for patients viraemic at week 2 [14]. There is no data available for this subgroup treated with sofosbuvir/velpatasvir. For all genotype 3 patients with decompensated cirrhosis, SVR was 50% after 12 weeks of sofosbuvir/velpatasvir [16], and 91% for patients with compensated cirrhosis [15]. Another study showed that a combination of 3 negative factors in genotype 3 patients dropped SVR after 12 weeks of sofosbuvir/velpatasvir to 85%, from 95% if only 2 negative factors were present [18].

Given the trial cohort will contain compensated and decompensated patients, the SVR after 12 weeks is estimated at 65%. The study assumes an SVR of 95% with the extended arm, in order for the margin of improvement to be clinically and statistically significant, as well as cost-effective to justify the increased drug costs. This is a realistic assumption given 12 weeks of sofosbuvir/velpatasvir in genotype 3 patients without negative factors (i.e. without cirrhosis) achieved SVR of 97% [15]. This study will demonstrate if treatment extension can overcome the impact of negative treatment factors on SVR.

To detect a true difference between the two treatment arms (if one exists) with 80% power and 95% confidence level, 24 participants are required as a minimum in each arm. The study will recruit 60 participants to allow for withdrawals or those lost to follow up.

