# 19.11 Procedure(s) to account for missing or spurious data

To reduce missing data on the primary outcome, SVR12 will be defined as HCV RNA <15iu/mL from 12 to 16 weeks after end of treatment. This widens the window when SVR12 can be reported. A negative HCV RNA at any point after 12 weeks post-treatment is clinically considered to be a sustained virological cure. Negative HCV RNA at less than 12 weeks post-treatment will be considered non-SVR12.

Non SVR12 will be differentiated by true viral relapse or missing data due to lost to follow up, to allow per-protocol analysis.

Given data is time point specific, data outside of the defined window cannot be carried forward to replace missing data.

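### Allocation may be issued up to four weeks before the arms diverge, so losses during the shared NHS course can fall after randomisation and, as the analysis set is written, may be counted differently in the two arms.

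*Protocol*

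**What the plan says.** Section 11.6 puts consent, screening and randomisation in one window starting at treatment week 8: "Screening and randomisation can take place until the end of standard treatment at week 12". Section 13.5.1 repeats it: "This takes place anytime after enrolment between treatment week 8 to 12". During that window the arms are treated alike. Section 15.1 says of all participants that "they will continue to take the dispensed supply between weeks 8 to 12", and only the 24-week arm (Arm B) receives anything further, from week 13.

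Section 13.9 foresees departures in this period: "If a participant withdraws during treatment week 8-12, while taking the NHS-supplied sofosbuvir/velpatasvir" opens its instruction on what happens to the tablets. The 90% adherence requirement (12.2, 13.4) is applied at screening.

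On analysis, sections 19.5 and 19.10 define intention to treat as all randomised participants with at least one dose of study drug. Sections 11.1 and 19.5 add, for the 24-week arm only, at least one extension dose. Section 19.11 places missing outcomes among the failures: "Non SVR12 will be differentiated by true viral relapse or missing data due to lost to follow up".

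The sample size (19.1) assumes a case "where SVR in the 12 week treatment arm is 65%, and 95% in the 24 week treatment arm" and states that "with 80% power and 95% confidence level, 24 participants are required as a minimum in each arm". It then adds: "The study will recruit 60 participants to allow for withdrawals or those lost to follow up".

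**The concern.** Nothing distinguishes the arms until the first week-13 tablet. A death, withdrawal or loss before then carries no information about treatment duration. If allocation has already been issued, however, that participant belongs to an arm and must be handled somehow.

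There are two ways this can hurt. Under the analysis set as written, an Arm B participant lost before week 13 has no extension dose and drops out of the primary comparison. An Arm A participant lost at the same moment may stay in as a failure. That asymmetry favours 24 weeks. If instead every randomised participant is analysed with missing as failure, the losses fall on both arms and shrink the difference.

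Of the reasons in 11.6, time to consider, selection of adherent patients and avoidance of drug wastage all support late consent. None needs allocation at week 8. Only the lead time for dispensing week-13 drug argues for early allocation.

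**Working it through.** **Inputs.** From 19.1: SVR12 65% and 95%, 80% power, 95% confidence (taken as two-sided 5%), minimum 24 per arm, 30 recruited. From 19.5: chi-square test (taken as uncorrected). Let d be the proportion lost between allocation and week 13. The protocol gives no value, so d is an assumption, and losses are taken as equal in the arms and unrelated to outcome.

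**Reproducing the plan's figure.** With unpooled variance, n = (1.960 + 0.842)² × (0.65×0.35 + 0.95×0.05) / 0.30² = 23.98, so 24 per arm. Exact power of the uncorrected chi-square is 80.8% at 24 per arm and 88.0% at 30. The step from 24 to 30 corresponds to 20% loss (24/0.80 = 30).

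**Reading 1: 19.5 as written, with NHS tablets counted as study drug in Arm A.** Arm A receives no other tablets, so without this reading it would have no analysis set. Section 15.4 nevertheless calls weeks 8 to 12 standard therapy, so the point is not settled. Take a true SVR12 of 65% in both arms. Arm A is analysed at 0.65(1−d) with n = 30. Arm B is analysed at 0.65 among those retained, their number being binomial(30, 1−d). The spurious difference is 0.65d: 3.25 points at d = 5% and 6.5 points at 10%.

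| d | Exact rejection rate with no true difference |
|---|---|
| 0 | 4.8% |
| 2% | 5.2% |
| 5% | 6.0% |
| 10% | 8.2% |

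**Reading 2: all randomised analysed, missing counted as failure.** The rates become 0.65(1−d) and 0.95(1−d), so the difference is 0.30(1−d), for example 28.5 points at d = 5%. The number per arm stays at 30, and the extra recruits do not restore the diluted difference.

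| d | Exact power, 30 per arm |
|---|---|
| 0 | 88.0% |
| 1% | 85.5% |
| 2% | 83.1% |
| 3% | 80.8% |
| 5% | 76.3% |

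Power crosses 80% at d of about 3.3% (exact). The normal approximations put the crossing at 4.1% (unpooled) and 2.3% (pooled).

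**Reading 3: losses excluded in both arms.** At 20% loss, 24 per arm remain and the unpooled power is 80.0%. The allowance in 19.1 covers this case.

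**What d might be.** The only discontinuation figure for this drug is in 9.1: 0.2% for adverse events over 12 weeks, in patients with or without compensated cirrhosis. Pro rata, 0.2% × 4/12 is about 0.07% in four weeks, which costs about 0.2 points of power under reading 2. As an upper illustration, suppose the whole 20% allowance were used at a constant rate. The four-week loss would be 1 − 0.8^(4/28) = 3.1% or 1 − 0.8^(4/16) = 5.4%, using the 28-week and 16-week participation in 11.6. That applies only if everyone is randomised on the first permitted day. With randomisation spread evenly over the window, the mean losses are 1.6% and 2.7%, and power is 84.1% and 81.4%.

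**The case against.** A reader might infer that the window costs the trial its stated power. The documents do not support that. The stated 80% belongs to 24 per arm, and the 88.0% from which power falls is never claimed. Four weeks is the maximum gap, and section 19.2 does not expect withdrawal to be a major problem. Treating the 24-to-30 allowance as an expected loss rate turns a contingency into a forecast. This objection stands.

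Nor is a departure always a missing outcome. Under 13.9, participants who stop treatment may stay in follow-up. Those who withdraw may finish the NHS tablets on their clinician's advice, and their SVR12 may be collected with consent. This also stands and lowers the effective d. On the other side, the 0.2% figure covers adverse events only, while section 12.1 admits decompensated cirrhosis and hepatocellular carcinoma, so the true d may be higher.

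A reader might also infer that knowing the allocation early changes adherence in the last shared month. In an open-label trial that is possible, but the protocol gives no figure for it, and missed doses are recorded at week 12 in both arms.

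Finally, early allocation has a stated practical reason: week-13 drug must be dispensed without interruption. This limits how late allocation can be, but it does not require week 8, since the protocol already accepts randomisation up to week 12.

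**Conclusion.** The point holds as a design weakness of uncertain and probably modest size. Allocation can precede any treatment difference by up to four weeks, and losses in that gap are unrelated to duration.

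Under the analysis set as written, the main harm is a one-sided exclusion favouring 24 weeks. It raises the rejection rate under no difference from 4.8% to about 6.0% at 5% loss and 8.2% at 10%. This rests on NHS tablets counting as study drug in Arm A. With all randomised participants analysed and missing as failure, the harm is dilution, and power stays at or above 80% until loss reaches about 3.3%. That threshold rests on the uncorrected chi-square and the 65% versus 95% assumption.

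Every loss rate used here is assumed. Loss of the stated power is not shown and should not be claimed. The case for change is that the noise is avoidable at little cost.

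**What to change.** In 11.6 and 13.5.1, separate screening from allocation. Keep consent and screening from treatment week 8. Have the coordinating centre issue the allocation as late in the week 8 to 12 window as the site's dispensing lead time allows, for example in the last 7 days of NHS supply. Precede it with a brief contact that confirms willingness and repeats the missed-dose check against the existing 90% criterion. Record anyone lost earlier as not randomised in the log that 13.4 already requires.

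In 11.1, 19.5 and 19.10, analyse all randomised participants under one rule for both arms. Late allocation shrinks the gap but does not remove it: an Arm B participant can still be lost between allocation and the first extension dose.

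The cost is mainly wording. Site pharmacies get shorter notice of who needs extension supply, and the existing requirement for uninterrupted supply must still be met. No visit is scheduled between screening and week 12, so participants screened early need one short re-contact. A few consented participants will not be randomised.

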#### Arm A (12 weeks of sofosbuvir/velpatasvir)

Screening / baseline (treatment week 8 up to week 12)

Randomisation by coordinating centre

Treatment week 12 (end of study treatment)

Treatment week 16 (post treatment week 4)

Treatment week 20 (post treatment week 8)

Treatment week 24 (post treatment week 12 – study endpoints & end of study)

## Arm B (24 weeks of sofosbuvir/velpatasvir

Screening / baseline (treatment week 8 up to week 12)

Randomisation by coordinating centre

Treatment week 12

Treatment week 16

Treatment week 20

Treatment week 24 (end of study treatment)

Treatment week 28 (post treatment week 4)

Treatment week 32 (post treatment week 8)

Treatment week 36 (post treatment week 12 – study endpoints & end of study)

## 11.7 Study Setting

Multi-site study within NHS England, with approximately 5 sites planned:

- Royal London Hospital, London
- Royal Free Hospital, London
- St Mary's Hospital, London
- King's College Hospital, London
- St George's Hospital, London

These sites are selected based on their role as leads or 'hubs' for the regional NHS HCV treatment programme, or 'Operational Delivery Network (ODN)'. They are also experienced clinical trial centres. Hub sites host regular (usually weekly) multidisciplinary team meetings to decide HCV management decisions for patients within the ODN, which may consist of patients from different hospitals within the same NHS Trust, or patients from hospitals within the geographical region but of another NHS Trust.

NHS England mandates that every patient started on direct acting antivirals (including sofosbuvir/velpatasvir) treatment is managed through an MDT, such that treatment decisions which may include participation in clinical trials, can be openly considered, and there is equity of access to expertise regardless of the location of the patient.

Through this NHS infrastructure, patients potentially eligible for the study will be identified through the usual care pathway. The study will recruit from 5 NHS 'hubs', which manages patients referred in from hospitals within the Operational Delivery Network, thus increasing the reach of the study. Enrolled participants will be treated at the study site (i.e. hub site) which leads the ODN they belong to, regardless of their referring hospital.

The Trial Steering Committee will review recruitment during the trial period (e.g. at around month 6) and if recruitment is inadequate, additional sites outside of London which are NHS England treatment hubs will be considered.

## 12.0 Eligibility Criteria

#### 12.1 Inclusion Criteria

A total of 60 participants will be enrolled. Participants must meet all of the following criteria to be eligible:

- Voluntarily signed informed consent form
- Aged 18 years or older
- Chronic HCV infection, defined by anti-HCV antibody or HCV RNA detection for greater than 6 months
- Infected with genotype 3 HCV (identified by referring hospital)
- Meets NHS England treatment criteria to commence sofosbuvir/velpatasvir
- Pre-treatment HCV RNA >10,000 iu/mL (can be any time before treatment week 0)
- HCV RNA > or equal to 30 iu/mL at treatment week 2 (+/- 3 days)

- Has cirrhosis defined by: evidence of portal hypertension, OR APRI >2 plus AST:ALT ratio >1,
  OR radiological evidence of cirrhosis, OR fibroscan score >11.5kPa, OR liver biopsy showing
  cirrhosis
- Patients with decompensated cirrhosis (variceal bleeding, ascites and encephalopathy) can be included
- Patients with malignancy including hepatocellular carcinoma can be included
- Patients with liver transplant can be included
- Patients coinfected with chronic hepatitis B virus or human immunodeficiency virus can be included
- Female subjects of childbearing potential must have documented negative pregnancy test prior to enrolment (negative urinary pregnancy test), and if engaged in heterosexual intercourse must use protocol specified method of contraception (see below) during study drug treatment and for 30 days after last dose
- Male subjects engaged in heterosexual intercourse with a female of childbearing potential should protocol specified method of contraception during study drug treatment and for 30 days after last dose

#### 12.2 Exclusion Criteria

- Any of the above inclusion criteria not met
- Any of the following criteria excludes a subject from enrolling into this study
- Clinically-significant medical or psychiatric illness (other than chronic HCV) in the past, present, or being evaluated, that may interfere with participant treatment, safety, assessment or compliance with the protocol.
- Severe renal impairment with eGFR <30 mL/min/1.73m^2 or requiring dialysis
- Alcohol consumption or illicit drug abuse likely to interfere with participant treatment, safety, assessment or compliance with protocol, as deemed by the investigator
- Previous exposure to sofosbuvir (or other NS5B inhibitor) or NS5A inhibitor
- Severe allergy to study drugs, its metabolites or formulation excipient (see SmPC for details)
- Any investigational medicinal product ≤ 6 weeks prior to treatment start
- Pregnant or nursing female, or males wishing to conceive during the period of study treatment + 30 days after
- Patients who adhered to less than 90% of prescribed sofosbuvir/velpatasvir at screening
- In accordance with the SmPC of sofosbuvir/velpatasvir concomitant use of the following medications are contraindicated:

Anticonvulsants - carbamazepine, phenytoin, phenobarbital, oxcarbazepine

Antimycobacterials - rifampicin, rifabutin, rifapentine

Antiretrovirals - efavirenz

St John's wort

Modafinil

Proton-pump inhibitors should be avoided and if necessary, should be administered 4 hours after at maximum doses equivalent to 20mg omeprazole per day.

Amiodarone should be avoided and if necessary, close monitoring is required

Please consult the SmPC and Section 15.16 and 17 for list of medications to be used with caution or monitoring.

Participants taking these medications must have discontinued prior to starting sofosbuvir/velpatasvir (this is expected to be in line with standard care practice). Definition of child-bearing potential and effective contraception:

Subjects are considered not of child-bearing potential if they are surgically sterile (undergone a hysterectomy, bilateral tubal ligation, or bilateral oophorectomy) or they are postmenopausal (women aged  $\geq$  45 years of age with cessation of previously occurring menses for  $\geq$  12 months) or they have medically-documented ovarian failure.

